### **7.3.3 Physical Examination and Vital Signs**

A physical examination including all major body systems is mandated at Screening and End of Treatment Visits only. During study treatment, symptom directed physical examinations will be performed.

Vital signs to be assessed include weight, body temperature, blood pressure, and pulse rate. Height will be recorded at screening only. In addition, blood pressure and pulse rate will be assessed every 30 minutes ( $\pm$  5 minutes) between the start and end of durvalumab infusions (periods of infusion interruption included) and, for the first infusion, for 1 hour post infusion.

Clinically significant findings noted during screening will be reflected on the medical history CRF, while those noted during study treatment will be collected on the AE CRFs.

### 7.3.4 Laboratory Safety Assessments

Laboratory safety assessments for which data will be collected in this study will include hematology, coagulation, thyroid tests, urinalysis and chemistry parameters presented in Table 13.

Laboratory tests will be drawn at the time points described in the Schedule of Assessment (Table 1) and analyzed at local laboratories. Additional laboratory tests may be performed per standard of care, at the investigator's discretion for the purpose of planning treatment administration, dose modification, following adverse events, or as clinically indicated.

**Table 13: Laboratory Safety Parameters**

Hematology Panel	Blood Chemistry Panel
Hemoglobin	Aspartate aminotransferase (ALT)
Platelet count	Alanine aminotransferase (AST)
White blood cell count (WBC)	Alkaline phosphatase
Neutrophil count	Lactate dehydrogenase (LDH)
Lymphocyte count	Total bilirubin (if Total bilirubin is $\geq 2 \times$ ULN and no evidence of Gilbert's syndrome, then fractionate into direct and indirect bilirubin)
Basophil count	Gamma glutamyltransferase Screening, C1D1, and as clinically indicated
Monocyte count	Lipase
Eosinophil count	Amylase
Coagulation	Creatinine
International normalized ratio (INR)	Blood urea nitrogen (BUN) or urea, depending on local practice
Prothrombin time (PT)	Uric acid
Partial thromboplastin time (PTT)	Total protein
	Glucose (non-fasted)
Urinalysis (dip stick)	Albumin
Blood	Calcium
Glucose	Sodium
Protein	Potassium
	Chloride
Thyroid Function Test	Magnesium
Thyroid-stimulating hormone (TSH)	Bicarbonate [ $\text{CO}_2$ ]
Free-T3 (if TSH abnormal)	
Free-T4 (if TSH abnormal)	

Pregnancy Testing: For patients of childbearing potential, a serum or urine pregnancy test will be performed at screening. Pregnancy tests will also be done whenever pregnancy is suspected during the study. Additional pregnancy testing may be necessary if required by local practices or regulations.

### **7.3.5 Electrocardiogram (ECG)**

Single and triplicate ECGs are to be performed as outlined in the Schedule of Assessments (Table 1). It is preferable that the machine used has a capacity to calculate the standard intervals automatically. In addition, QTc will be manually calculated using the Fridericia's formula. Assessments reported by automated read as prolongation of QTc should be over-read by a cardiologist to ensure accuracy of interpretation.

### **7.3.6 Echocardiogram (ECHO)**

Echocardiograms will be performed at screening, and thereafter as in the Schedule of Assessments (Table 1). Additional assessments of LVEF and evaluation of pericardial effusions may be performed as clinically indicated at the investigator's discretion if there are signs or symptoms of cardiotoxicity. Where abnormalities indicating pericardial effusion exist, weekly assessments should be performed until normalization as described in Section 5.1.8.5. In exceptional circumstances where ECHO is not considered a technically optimal assessment of pericardial space (e.g., overweight patient), other methods (e.g., MRI) should be used for pericardial assessments.

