15. History of interstitial lung disease (ILD), drug-induced ILD, radiation pneumonitis which required steroid treatment, or any evidence of clinically active interstitial lung disease.
16. History of stroke or transient ischemic attack within the previous 6 months.
17. Any of the following cardiac abnormalities:
  - a. Unstable angina pectoris,
  - b. Congestive heart failure  $\geq$  NYHA Class 3,

- c. QTc  $\geq$ 470 milliseconds on electrocardiogram (ECG) calculated using Frediricia's Correction, or
  - d. Current or history of a small, moderate or large pericardial effusion, and/or hemodynamic compromise due to pericardial effusion of any size. Minimal or trivial pericardial effusion is not excluded.
18. Concomitant medication known to cause prolonged QT which cannot be discontinued or changed to a different medication prior to enrollment.
19. Active brain metastases. Subjects are eligible if brain metastases are adequately treated and subjects are neurologically stable (except for residual signs or symptoms related to the CNS treatment) for at least 2 weeks prior to enrollment without the use of corticosteroids, or on a stable or decreasing dose of  $\leq$  10 mg daily prednisone (or equivalent).
20. Known or suspected presence of another malignancy that could be mistaken for the malignancy under study during disease assessments.
21. Pregnancy. WOCBP must have a negative serum or urine pregnancy test documented within the screening period prior start of study drug.
22. Breast-feeding or planning to breast feed during the study or within 6 months after study treatment.
23. Any psychiatric illness/social situations that would limit compliance with study requirements or compromise the ability of the patient to give written informed consent.
24. Any serious illness, uncontrolled inter-current illness, active or uncontrolled infection, or other medical history, including laboratory results, which, in the Investigator's opinion, would be likely to interfere with the patient's participation in the study, or with the interpretation of the results.

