#### 5.1.8.5 Management of Mocetinostat in Event of Pericardial Toxicity

Patients will be assessed for evidence of pericardial toxicity during scheduled visits according to the Schedule of Assessments (Table 1).

The following findings would heighten suspicion of pericardial effusion or pericarditis and prompt immediate evaluation by ECHO:

- Symptoms: shortness of breath, orthopnea, chest pain, dizziness, rapid pulse
- Clinical exam: hypotension, jugular venous distension, pulsus paradoxus, faint heart sounds, friction rub, and/or arrhythmia

- ECG: sinus tachycardia, atrial fibrillation, atrial flutter, low voltage with nonspecific ST-T wave changes and ST elevation or PR depressions, arrhythmia

ECHOs will be used to assess and categorize pericardial fluid as minimal (or trivial), small, moderate or large and will assess for hemodynamic compromise.

Pericardial effusions will be assessed and managed as follows (Table 8):

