**Table 8: Pericardial Effusion and Patient Management Guidelines**

Category	Definitions	Patient Management
Minimal (or trivial)	A small echo-free space in the posterior atrioventricular groove that is visible only in systole when the heart has pulled away from the pericardium. Typically represents a normal amount of pericardial fluid in a disease-free state.	De novo (i.e., not present at baseline) pericardial effusion: 
 
• Study treatment may be continued at the discretion of the investigator.
 
• Increased ECHO and ECG monitoring weekly until effusion is no longer present or has not progressed over a period of 2 weeks.
 
• Regular assessment schedule afterwards.
 

Small	< 1 cm of posterior echo-free space, with or without fluid accumulation elsewhere, present throughout the cardiac cycle, including diastole (and not only systole).	
 
• Study drug will not be discontinued in these Patients, at the discretion of the investigator, unless the effusion progresses.
 
• Increased ECHO and ECG monitoring weekly for the first month after the new effusion first noted or until the effusion has regressed (if sooner).
 
• Treatment for the effusion may be administered at the discretion of the Investigator.
 

Moderate	1 to 2 cm of echo-free space. Moderate effusions tend to be seen along the length of the posterior wall but not anteriorly.	
 
• Remove immediately from study treatment.
 
• Manage according to the standard of care at the discretion of the investigator.
 
• Refer to cardiologist for follow-up as clinically indicated, until resolution of stabilization.
 

Large	> 2 cm of maximal separation. Large effusions tend to be seen circumferentially.	

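### Protocol Section 7.3.6 runs weekly effusion monitoring to normalization, but Table 8 in the section it cites stops at other endpoints, so follow-up of a persistent small effusion depends on which text a site follows

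*Protocol*

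**What the plan says.** Protocol Section 7.3.6 places echocardiograms on the Table 1 schedule and adds: "Where abnormalities indicating pericardial effusion exist, weekly assessments should be performed until normalization as described in Section 5.1.8.5". It gives no size category and no time limit.

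Section 5.1.8.5 manages effusions through Table 8, which sets follow-up by size:

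- Minimal or trivial, and new since baseline: "Increased ECHO and ECG monitoring weekly until effusion is no longer present or has not progressed over a period of 2 weeks", then "Regular assessment schedule afterwards".
- Small: "Increased ECHO and ECG monitoring weekly for the first month after the new effusion first noted or until the effusion has regressed (if sooner". The patient may stay on study drug, at the investigator's discretion, unless the effusion progresses.
- Moderate or large, and hemodynamic compromise: removal from study treatment and cardiology follow-up as indicated, ending at resolution or stabilization. No ECHO interval is stated.

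Table 1 schedules ECHO at screening, Cycle 1 Day 15, Day 1 of Cycle 2 and each later cycle, and end of treatment. Exclusion criterion 17.d allows entry with trivial fluid: "Minimal or trivial pericardial effusion is not excluded".

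**The concern.** Section 7.3.6 attributes to Section 5.1.8.5 an endpoint that Section 5.1.8.5 does not contain. A site with a small effusion unchanged after five weeks reads one text as continuing weekly imaging and the other as having ended it. Nothing in the protocol gives either text precedence.

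The subject is not incidental. Pericardial findings are the only entry under the mocetinostat heading for adverse events of special interest (Section 8.3.3.2), and all are reported by the expedited route. Section 1.4 says an immune-based mechanism is possible and that adding durvalumab may raise the risk. Section 1.2.3 says most earlier mocetinostat trials did not screen for pericardial events. In Table 8 a small effusion is compatible with continued treatment and a moderate one is not, so repeat imaging feeds directly into a rule for removal from treatment.

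**Working it through.** The plan gives no figure to reproduce. The check sets the passages side by side and then counts visits.

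**Endpoints for weekly monitoring**

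| Effusion | Section 7.3.6 | Table 8 |
|---|---|---|
| Minimal, new | Normalization | Gone, or 2 weeks without progression; then regular schedule |
| Small | Normalization | First month, or regression if sooner |
| Moderate, large, hemodynamic compromise | Normalization | No ECHO interval stated |

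For the small row, one month is a ceiling whether or not the effusion persists. For the minimal row, a stable effusion that is still present meets the stopping condition. Neither is normalization.

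**Visit count for a persistent small effusion**

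Assumptions: first seen at Cycle 1 Day 15, stable, patient on treatment a further 24 weeks, first month taken as 4 weeks, later ECHOs on cycle Day 1 as in Table 1.

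- Section 7.3.6: 24 weeks × 1 per week = 24 ECHOs.
- Table 8: 4 weekly ECHOs (the Cycle 2 Day 1 ECHO coincides with the second), then Day 1 of Cycles 3 to 7, which is (24 − 4)/4 = 5. Total 4 + 5 = 9.

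**Detection gap**

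Cycle Day 1 visits from Cycle 2 on fall at study days 29, 57, 85 and so on, counted from Cycle 1 Day 1. Weekly scans counted from day 15 coincide with them: (29 − 15)/7 = 2, (57 − 15)/7 = 6, (85 − 15)/7 = 10. Once the Table 8 patient is on the cycle schedule, the worst case is progression just after a shared scan. It is seen after 7 days under one text and 28 days under the other, a difference of 28 − 7 = 21 days, or about 3 weeks before visit windows.

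**Shorter illustration, including the minimal row**

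Assumptions: effusion first seen at week 0, stable through week 12, regular ECHOs at weeks 4, 8 and 12.

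- Section 7.3.6: weeks 1 to 12, 12 ECHOs.
- Table 8, small: weeks 1 to 4, 8 and 12, 6 ECHOs.
- Table 8, minimal: weeks 1, 2, 4, 8 and 12, 5 ECHOs.

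The difference grows with persistence. It is nil if a small effusion normalizes within the first month.

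**The case against.** The best defence is that Section 7.3.6 is a loose paraphrase with a pointer. It says weekly assessments should be done as Section 5.1.8.5 describes, so a careful site would go to Table 8 and follow the size-specific row. Table 8 also does not forbid extra scans, and Section 7.3.6 itself allows additional assessments when clinically indicated. This is a plausible reading, but the sentence still names an endpoint that the cited section lacks. A site that takes it at its word is not misreading it.

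Three further points stand and limit the size:

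- Section 5.1.8.5 calls for immediate ECHO on listed symptoms, examination signs or ECG findings under either text. The gap therefore concerns only progression without any of these.
- Section 1.2.3 says most pericardial events occurred in the first cycle and most findings resolved completely. Twenty-four weeks of a stable effusion is a long illustration, not a typical course.
- Section 7.3.6 says should, not must.

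A reader might infer more than the documents support:

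- That the texts also collide for moderate or large effusions. Table 8 is silent there on ECHO frequency, and weekly imaging would satisfy both texts.
- That patients entering with minimal fluid go on weekly ECHO from the start. Section 7.3.6 is triggered by abnormalities, while Table 8 says of this category: "Typically represents a normal amount of pericardial fluid in a disease-free state". Its minimal row covers only effusions absent at baseline.
- That detection could differ by 4 weeks. With aligned scans the difference is 21 days.
- That reported effusion frequency would shift between sites. Weekly monitoring starts only after an effusion is found, and SAP Section 12.6.1 counts each patient once per preferred term.

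**Conclusion.** The text is wrong as written. This is an internal inconsistency, not a matter of design choice. It is firm for small effusions, where one text ends at normalization and the other at one month or regression. It is also present for new minimal effusions, although there one can argue that typically normal fluid does not trigger Section 7.3.6.

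The practical effect is an imaging interval of 7 against 28 days for a persistent, stable small effusion in a patient still on drug, and a delay of up to about 3 weeks in detecting otherwise silent progression. The 24 against 9 count rests on the assumptions stated with it: first detection at Cycle 1 Day 15, stability for 24 weeks, and a 4-week month. The inconsistency changes no primary endpoint, sample size or removal threshold. It deserves correction because the imaging interval determines when the removal rule can be applied.

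**What to change.** Reconcile Section 7.3.6 with Table 8 so that a single rule states, for each effusion size, when weekly ECHO and ECG end. Section 7.3.6 should then refer to that rule without giving an endpoint of its own. One added sentence could say whether the rule covers minimal fluid already present at baseline. Which rule applies is for the sponsor's clinical team to decide; this review takes no position on it.

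The cost is a wording change, by administrative letter or at the next amendment, with no visits beyond those in whichever rule is confirmed.

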## **7.4 Laboratory Studies**

Laboratory studies for which blood will be collected include evaluation of PK, ADA, and PD. The schedules for sample collection are outlined in Table 2. Blood samples will be collected using an in-dwelling catheter or venipuncture into specified vacutainer tubes. Full details on sample collection, processing, storage and shipment are presented in the Study Laboratory Manual.

### **7.4.1 Pharmacokinetic Evaluation**

The PK of mocetinostat and durvalumab will be determined using plasma samples collected at specified time points prior to and following study treatment dosing. Every effort will be made to collect these PK samples at the exact nominal times relative to dosing. A variation window is allowed for each time point as outlined in Table 2. The actual time of each sample collection will be recorded on the source document and CRF.

All plasma samples will be stored frozen and shipped on dry ice according to instructions provided. Analysis of plasma samples will be performed using specific validated bioanalytical methods. Full details on sample collection, processing, storage and shipment will be provided in the Study Laboratory Manual.

#### **7.4.2 Anti-Drug Antibody Evaluation**

Blood samples for measurement of durvalumab ADA concentrations in serum will be collected in samples taken according to the schedules of study procedures presented in [Table 2](#). Details for collection, aliquoting, storage, and shipment of serum samples for ADA evaluations are presented in a separate Laboratory Manual. Validated electrochemiluminescence assays using a Meso Scale Discovery platform will be used for the determination of ADAs to durvalumab in human serum.

#### **7.4.3 Pharmacodynamic Evaluation in Tumor Tissue**

Pharmacodynamic parameters in tumor tissue that may be investigated in this study include but are not limited to PD-L1 expression, CD8+ TILs, NK-cells, Tregs, and MDSCs, prior to and during treatment. Full details on sample collection, processing, storage and shipment will be provided in the Study Laboratory Manual.

#### **7.5 Post-treatment Follow-up**

Blood samples for MEDI4736 PK and ADA will be collected approximately 90 days after the last infusion of durvalumab. Survival status and subsequent therapies will be collected during long term follow-up as outlined in the Schedule of Assessments ([Table 1](#)) until death or lost to follow-up. Beyond 90 days after last treatment, follow-up may be performed by telephone contact. Treatments received following participation in the study will be collected in the CRF.

## **8 ADVERSE EVENT REPORTING**

### **8.1 Sponsor Medical Monitor Personnel**

The contact information for the sponsor's Medical Monitor personnel for this trial is available in the study contact list located in the Study Manual.

### **8.2 Adverse Events**

An adverse event (AE) is any reaction, side effect or other undesirable medical event that occurs during participation in a clinical trial, regardless of treatment group or suspected causal relationship to study treatment. A treatment emergent AE (TEAE) is an AE that occurs after the first dose of any study treatment or any preexisting condition that increases in severity after the first dose of study treatment.

All observed or volunteered AEs will be recorded in source documents and reported in the CRF. The best available medical terminology should be used to describe AEs in source documents and CRFs. Terms describing the diagnosis are preferred over individual signs and symptoms of the diagnosis. If determination of the diagnosis is delayed, record signs and symptoms and add the diagnosis as an AE when available; follow all recorded AEs to resolution. Examples of AEs include but are not limited to:

- Signs or symptoms of co-morbidity, illness, or toxicity of study treatment;
- Signs or symptoms of worsening malignancy under study (disease progression assessed by measurement of malignant lesions should not be reported as an AE).
- Laboratory abnormalities (see [Section 8.2.1](#) for guidance for reporting in CRF);
- Hypersensitivity;
- Drug abuse, dependency, overdose, withdrawal or misuse;
- Signs or symptoms of drug interactions;
- Extravasation;
- Exposure during pregnancy or via breastfeeding;
- Medication error; or
- Occupational exposure.

### **8.2.1 Laboratory Abnormalities**

An abnormal laboratory test results should be reported as an AE in the CRF only if it is associated with one or more of the following:

- Clinical symptoms;
- Requires additional tests (beyond repeats), treatment or intervention;
- Results in change in study treatment dosing;
- Requires discontinuation from study treatment; and/or
- Considered by the investigator or Sponsor to be an AE.

#### **Hy's Law**

Hepatic function abnormality is defined as any increase in ALT or AST to greater than  $3 \times \text{ULN}$  and concurrent increase in total bilirubin to be greater than  $2 \times \text{ULN}$ . Concurrent findings are those that derive from a single blood draw or from separate blood draws taken within 8 days of each other. Follow-up investigations and inquiries will be initiated promptly by the investigational site to determine whether the findings are reproducible and/or whether there is objective evidence that clearly supports causation by a disease (e.g., cholelithiasis and bile duct obstruction with distended gallbladder) or an agent other than the investigational product.

Cases where a patient shows an AST or ALT  $\geq 3 \times \text{ULN}$  and total bilirubin  $\geq 2 \times \text{ULN}$  may need to be reported as SAEs. These cases should be reported as SAEs if they meet the criteria for a Hy's Law case or if any of the individual liver test parameters fulfill any of the SAE criteria. Additionally, study drug should be permanently discontinued for a Hy's Law case.

### **8.2.2 Severity Assessment**

AEs occurring during this study will be graded in accordance with the National Cancer Institute Common Terminology Criteria for Adverse Events (CTCAE, Version 4.03). Documentation of AE grading in the source documents and CRF should be consistent with provided definitions.

### **8.2.3 Causality**

For each AE, the investigator should determine and document whether there exists a reasonable possibility that the study treatment caused or contributed to the AE. The investigator's assessment should be recorded in the source document. The CRF will provide the options for attribution to study treatment as "related" and "not related." If the investigator's causality assessment is "unknown but not related to investigational

product," this should be recorded in the CRF as "not related." If the investigator does not know whether or not the study treatment is causally-related to the event, reporting for study purposes will be as "related" to study treatment.

Collection of causal relationship for AEs associated with study procedures (e.g., tumor biopsy) is provided for separately in the CRF.

### **8.3 Serious Adverse Events**

#### **8.3.1 Definition of a Serious Adverse Events**

An SAE is any event that meets any of the following criteria:

- Results in death;
- Is life-threatening (immediate risk of death);
- Requires inpatient hospitalization or prolongation of existing hospitalization;
- Results in persistent or significant disability/permanent damage (substantial disruption of the ability to conduct normal life functions);
- Results in congenital anomaly/birth defect.
- Other: Important medical events that may not result in death, be life-threatening, or require hospitalization, may be considered an SAE when, based upon appropriate medical judgment, they may jeopardize the patient and may require medical or surgical intervention to prevent one of the outcomes listed in this definition. Examples of such events are:
  - Intensive treatment in an emergency room or at home for allergic bronchospasm
  - Blood dyscrasias or convulsions that do not result in inpatient hospitalization
  - Development of drug dependency or drug abuse

Progression of the malignancy under study, including any signs or symptoms of progression that may require hospitalization, should not be reported as an SAE unless the outcome is fatal within the safety reporting period.

